1.5.3 Management of patients presenting with locoregional recurrence with distant metastasis

There are further management options emerging for patients who present with LRR and distant metastasis. Traditionally these patients were not considered for surgical resection of the LRR, except in cases where surgery would provide palliation (e.g. where a fungating tumour was bleeding, painful or difficult to manage with dressings). However, small numbers of patients are currently being managed with surgical resection of the LRR in the presence of distant metastatic disease[54]. This is especially relevant with advances in systemic therapy (e.g. anti-HER2 therapies and CDK inhibitors), which may enable some patients with metastatic breast cancers to undergo LRR resection if deemed to have good response to systemic therapy or for local control with palliative intent. Breast surgery to the primary cancer in the presence of distant metastasis has been evaluated in Austria (ABCSG-28 POSYTIVE trial[54]), India[55] and Turkey (MF07-01 trial[56]) with conflicting survival benefit observed. Currently in the UK, it is not known how many patients are undergoing surgery for LRR in the presence of distant metastasis. Therefore, a national database to record their management and survival outcomes would be of value and can be compared against the patients with LRR without distant metastasis.

1.5.4 Adjuvant therapy options

Cancer recurrence may be due to survival and proliferation of clones that are resistant to a range of adjuvant therapies. Therefore, it would be of interest to examine the choice of endocrine and/or chemotherapy in patients with LRR. The CALOR trial demonstrated that patients with ER- (but not ER+) locally recurrent cancer benefited from further chemotherapy[57]. This randomised control trial demonstrated improved 5 year disease free survival (69% versus 57%) and overall survival (88% versus 76%) for patients who received chemotherapy after LRR resection surgery. There is also an increasing role for partial breast radiotherapy in patients treated with repeat BCS who have had previous BCS and radiotherapy[58]. Compared to treatment for primary breast cancer, there is a relative lack of clinical trial data on the efficacy of further adjuvant systemic therapy in patients diagnosed with LRR. The MARECA study will gather data on the type of adjuvant treatments currently used to treat patients diagnosed with LRR in the UK.

Given the complexity mentioned so far in the multidisciplinary management of patients with LRR, there is a need to examine long term oncological outcome and determine optimal patient management. The current literature reporting survival outcome for patients diagnosed with LRR are mostly based on single institution retrospective studies with

significantly different reported patient outcomes; a 5 year disease free survival (DFS) rate of 48 to 67% has been reported, and an equivalent overall survival (OS) rate of 61 to 82% has been reported[59]. Furthermore, these published studies are over 10 years old, reflecting the need to perform a prospective study to determine patient outcome, which reflects modern breast cancer treatment.

One of the key aim of the MARECA study will be to identify which patient groups are at most risk of further LRR, distant metastasis, and subsequent mortality after their treatment of LRR. A notable study in 2009 reported OS rates for patients with node negative cancer who were treated by BCS and WBRT as part of the NSABP protocols of node negative breast cancer[60]. They reported worse OS outcome in patients who presented with recurrences in the regional lymph nodes, as opposed to recurrences in the conserved breast (5 year OS of 34.9% versus 76.6% respectively). In addition, shorter interval time between the initial and recurrent cancer diagnosis has been identified as a poor prognostic factor for patients diagnosed with LRR[61]. By evaluating the tumour characteristics and treatment patterns of the initial and recurrent cancer, MARECA study will aim to identify other predictive prognostic factors for patients diagnosed with LRR. This will in turn guide clinicians with an aim of optimising patient management and improve treatment outcomes.

2. Aims and Objectives

2.1 Study design

The MARECA study is a prospective, observational, multicentre, longitudinal cohort study.

2.2 Aims

The MARECA study will determine the frequency, current management and prognosis of patients diagnosed with breast cancer locoregional recurrence in the UK with the aim of establishing best practice and informing future national guidelines.

2.3 Objectives

 To carry out a national survey of UK breast units in order to establish the current stated practice of breast MDTs regarding the management of patients with locoregional recurrence and identify any potential geographical variations. 2. To establish a prospective cohort of breast cancer patients diagnosed with locoregional recurrence +/- distant metastasis in order to:

- i) Describe current management including:
 - Use of radiological staging investigations and the proportion of patients found to have distant metastasis (DM) at presentation.
 - Surgical management including the use of repeat BCS and SLNB.
 - Use of systemic therapies and radiotherapy used to treat locoregional recurrence.
- ii) Investigate risk factors associated with LRR development including those related to the primary breast cancer and its management.
- Determine the following oncological outcome at 3 and 5 years, and evaluate prognostic factors;

-Disease Free Survival (DFS) for patients diagnosed with LRR without associated distant metastasis at presentation.

-Progression Free Survival (PFS) for patients diagnosed with LRR with associated distant metastasis at presentation.

-Overall Survival (OS) for patients diagnosed with LRR with or without associated distant metastasis at presentation.

 iv) Stratify LRR as a true recurrence (TR) or a new primary (NP) breast cancer using clinical classification systems and explore if this distinction affects oncological outcomes.

3. To determine the feasibility of designing a future potential translational study. Patients enrolled in the study will be invited to provide optional consent for permission to access archival tissue samples (or slides) of both the primary cancer and the locoregional recurrence. This would permit comparison of clinical and genomic classification of locoregional recurrences (true recurrence or new primary) against patient survival outcome.

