[name] Consultant Oncoplastic Breast Surgeon St. James's University Hospital, Leeds Co-investigator

[name] NIHR Clinical Lecturer in Surgery University of Sheffield Co-investigator

IRAS ID: 285389

2 The MARECA study Protocol ve

Protocol version 4.0 25/05/2022

Study overview

Although the 5 year breast cancer survival rate in the UK is considered favourable at 86.6%, patients continue to develop breast cancer recurrence within the same breast after breast conserving surgery, as well as in the remaining skin or chest wall after mastectomy. Patients also present with breast cancer recurrence in the nearby lymph glands (axilla, supra- or infra-clavicular, or internal mammary chains). These recurrences are collectively termed locoregional recurrence (LRR). It is estimated that up to 8% of breast cancer patients are diagnosed with LRR within 10 years of their original diagnosis.

Currently there is a lack of high-quality data and clinical guidance for the optimal management of breast cancer patients diagnosed with LRR. Additionally, there is a need to identify prognostic factors which will enable tailored treatment in order to improve patient outcomes. This was identified as a research priority at the 2019 Association of Breast Surgery Gap Analysis meeting. In the UK, breast cancer recurrence is under-reported to national cancer registries at individual hospital level (2020 annual report National Audit of Breast Cancer in Older Patients). As a result, retrospective analysis of existing routine data sources is unlikely to provide data on patient management that is representative of current national practice.

The MARECA study is a prospective, observational, multicentre, longitudinal cohort study which will determine LRR frequency and the current management and prognosis of patients diagnosed with breast cancer LRR +/- distant metastasis in the UK, with the aim of establishing best practice and informing future national guidelines. Over 50 UK breast units will participate in the study and recruit patients for 24 months with an aim of recruiting at least 500 patients. Data will be collected detailing the tumour pathology, imaging results, surgical treatment, radiotherapy, and systemic therapy of the primary and recurrent breast cancer.

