Establishing a prospective cohort of patients newly diagnosed with LRR +/- distant metastasis will enable description of current multidisciplinary patient management, identify any potential geographical variations in patient care, and investigate risk factors associated with LRR development (including those related to the primary breast cancer and its management). The study participants will be followed up at two time points (3 and 5 years) in order to determine oncological outcome and evaluate potential prognostics factors, including stratification of LRR as a true recurrence or a new primary breast cancer. Specifically, we will investigate whether the type of surgery performed for the primary breast cancer (breast conserving surgery and radiotherapy vs. mastectomy) influences subsequent prognosis in patients diagnosed with locoregional recurrence.

The study results will aim to address the current knowledge gap and identify subgroup of patients who have less successful treatment outcome. This will direct future research and inform the design of future interventional trials and translational studies.

Table of Contents

Study overview		3
1. Background		6
1.1 The current national status		6
1.2 Known risk factors for locore	gional recurrence	8
1.2.1 The extent of surgery do	es not influence locoreg	ional recurrence rate8
1.2.2 The role of radiotherapy	in reducing locoregional	l recurrence rate9
1.2.3 Tumour biology and loco	pregional recurrence	9
		gional recurrence and evaluation
		cancer affect prognosis in patients 11
1.4 Definition of locoregional rec	currence as true recurrer	nce versus new primary12
1.5 Uncertainties in the treatmer	nt of locoregional recurre	ence13
1.5.1 Surgery- repeat breast c	conserving surgery vs. m	astectomy13

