4.3 Evaluation of the initial cancer management

Data collection about the original cancer management will aim to identify known risk factors for LRR (see section 1.2). This will involve examination of the tumour characteristic and the treatment received for the initial cancer. NICE guideline[35] on 'early and locally advanced breast cancer: diagnosis and management (NG 101)' provides recommendations about which patients should be offered particular adjuvant treatments based on the tumour

characteristics and the surgery performed. Therefore, the receipt of, as well as compliance with, the recommended adjuvant treatment will be explored with regards to the management of the patient's original cancer.

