4.6 Patient inclusion and exclusion criteria

4.6.1 Inclusion criteria

- Female or male patients more than 18 years old. Treated for previous unilateral or bilateral breast cancer (invasive cancer including all histological subtypes as well as ductal carcinoma in situ) with curative intent.
- No previous evidence of distant metastatic disease.
- Recently (within the last 6 months) diagnosed with new ipsilateral breast cancer locoregional recurrence (biopsy proven invasive cancer including all histological subtypes or ductal carcinoma in situ) +/- distant metastasis.
- Able to provide written informed consent.
- A *minimum of 3 months interval* between the resection surgery for the original cancer and the diagnosis of locoregional recurrence. There will be *no maximum interval time period*.

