7.3 Data recording and record keeping

All information collected during the course of the study will be kept strictly confidential. The information governance team (including the trust's Caldicott guardian) at Leeds Teaching Hospitals NHS Trust has reviewed the study protocol, and we have obtained Caldicott approval for the study.

Information will be held securely on paper and electronically at each participating NHS Trusts. All participating sites will comply with all aspects of the Data Protection Act 2018 and operationally this will include:

- consent from patients to record personal details including name, date of birth, address and telephone number, email address, NHS ID and hospital ID
- appropriate storage, restricted access and disposal arrangements for patient personal and clinical details
- consent from patients for access to their medical records by responsible individuals from the research staff, the sponsor, and from regulatory authorities, where it is relevant to trial participation
- Consent from patients for the data collected for the trial to be used to evaluate safety and develop new research.

Data completeness is an integral part of any study. A CONSORT style will be used to monitor data completeness from eligibility screening, approach, study acceptance through to the final follow-up visit. This information will be made available to the study steering group as regular reports. The team will also report the number of:

- Patients screened per month
- Patients approached per month (and reasons why not approached)
- Patients recruited per month
- The number of patients who complete each follow up visit or are lost to follow-up
- The number of patients who complete the trial.

8. Sample size and data analysis

All data analysis will occur centrally and will be led by the steering group. Local collaboratives and hospital trusts will have ownership of their own data and will be able to present it locally if they so wish. Summary statistics will be calculated for each participating Trust and fed back to individual units to allow comparison with national averages and ranges. It is important to note that we cannot determine locoregional recurrence rate for each unit or at national level. We will not have a denominator to determine this rate.

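### The protocol promises LRR frequency and risk factors for developing LRR, but a cohort made up only of LRR patients with no denominator can deliver neither

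*Protocol*

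**What the plan says.** **Frequency.** The overview says the study "will determine LRR frequency and the current management and prognosis of patients diagnosed with breast cancer LRR". Section 2.2 repeats this as the aim: "The MARECA study will determine the frequency, current management and prognosis of patients diagnosed with breast cancer locoregional recurrence in the UK". Section 8 then states that "we cannot determine locoregional recurrence rate for each unit or at national level" and gives the lack of a denominator as the reason.

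**Risk factors.** Objective 2(ii) in section 2.3 is to "Investigate risk factors associated with LRR development including those related to the primary breast cancer and its management". The overview repeats it, and section 1.1 says the collaborative dataset will allow risk factors for LRR to be identified.

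**Who is enrolled.** Section 4.6.1 requires every participant to be recently "diagnosed with new ipsilateral breast cancer locoregional recurrence". It sets a three-month minimum since the original resection and "no maximum interval time period".

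**What is planned in practice.** Sections 1.2.4 and 4.3 plan to record known risk factors in the enrolled patients and to set their original treatment against the NICE guideline (reference 35). Section 1.2.4 gives the purpose as understanding why LRR may have developed. Section 4.3 says "the receipt of, as well as compliance with, the recommended adjuvant treatment will be explored".

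**The concern.** Two stated goals go beyond what the design can give. A frequency needs a population at risk. An association with developing LRR needs either patients who did not develop it or the distribution of exposures among all treated primary cancers. The protocol provides neither.

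What is at stake is the study's conclusions. It is meant to inform national guidelines. If the aims stand as written, a feature that is merely common among primary cancers could be reported as a risk factor for recurrence because it is common among the cases. Likewise, treatment that differed from the guideline could be reported as a reason for recurrence, with no knowledge of how often the same difference occurred in patients who stayed free of recurrence.

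**Working it through.** **1. Frequency: the passages side by side.** The overview and section 2.2 say it will be determined; section 8 says the rate cannot be, for units or for the country. Section 1.1 presents the shortage of reliable data on the UK rate of LRR as part of the motivation, so the natural reading of frequency is a rate.

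**2. Would a count of recruits do instead?** Inputs from section 8: about 250 LRR patients across 15 units in 6 months; 5 to 10 recruits expected per unit per year; at least 50 of 144 UK units.

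- Eligible per unit per year = 250 / 15 × 2 = 33.3, which reproduces the protocol's figure of about 33.
- Expected capture = 5 / 33.3 to 10 / 33.3 = 15% to 30%.
- Recruitment at the lower figure = 50 × 5 × 2 = 500, which matches the target.

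On the protocol's own figures the recruited cohort is an incomplete numerator as well as lacking a denominator. The Appendix questionnaire asks each unit for its yearly number of new cancers and banded LRR numbers. These are estimates made by the multidisciplinary team, not follow-up of a population at risk, and no rate is planned from them.

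**3. Risk factors: what case-only data identify.** Let *c* be the share of LRR patients with an exposure and *s* the share of all treated primary cancers with it. If the cases are representative of all LRR,

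RR = (*c* / *s*) / [(1 − *c*) / (1 − *s*)].

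The study observes *c* but does not collect *s*. Section 1.3 cites series with 40% mastectomy and 60% breast conservation with radiotherapy among LRR patients, so *c* = 0.40. The values of *s* below are assumptions, chosen to show the range:

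| Assumed *s* | Calculation | RR, mastectomy vs conservation |
|---|---|---|
| 20% | (0.40/0.20) / (0.60/0.80) | 2.67 |
| 30% | (0.40/0.30) / (0.60/0.70) | 1.56 |
| 40% | (0.40/0.40) / (0.60/0.60) | 1.00 |
| 50% | (0.40/0.50) / (0.60/0.50) | 0.67 |
| 60% | (0.40/0.60) / (0.60/0.40) | 0.44 |

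The same case data fit a raised risk, no effect or a lowered risk. The argument is the same for grade, margins or omitted radiotherapy.

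**4. What remains estimable.** The prevalence of known risk factors among LRR patients, the treatment they originally received, and prognostic factors for outcome after LRR. The last compares patients within the cohort and needs no recurrence-free group.

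**The case against.** **Frequency is a stray word.** It appears in the overview and the aim, but not in the objectives, endpoints or analysis text, and section 8 warns the reader that no rate is available. It might also mean caseload, since section 7.3 plans monthly screening counts. This stands as to consequence: someone following section 8 would not report a rate. It does not remove the contradiction, and a count at participating units is not the frequency of LRR in the UK.

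**The working text is already descriptive.** Sections 1.2.4 and 4.3 speak of finding known risk factors in the cases, and section 8 specifies no model with LRR development as the outcome; its named survival outcomes are DFS, progression-free survival and overall survival. This also stands. A reader might infer that the plan prescribes an invalid risk-factor regression; it does not. The fault is that the objective claims more than the planned work can support.

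**The denominator admission covers the rate only.** Correct. A reader might take section 8 as conceding the risk-factor point too. It does not; that point rests on the eligibility criteria.

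**Guideline comparison.** Because there is no maximum interval, a reader might infer that many patients will be called non-compliant with guidance that postdates their treatment. The documents do not establish this. Compliance in section 4.3 can mean the patient's adherence to treatment, which fits data items 2.29 (endocrine duration) and 2.37 (chemotherapy stopped early). The only date for reference 35 is the 2018 update in its link, and nothing shows what earlier guidance said. Nor can the number of older cases be derived from the 5- and 10-year rates in sections 1.1 and 1.2.1, which come from different populations and endpoints. Handling by era may also be left to an analysis plan not shown.

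**Conclusion.** The point holds in two parts. The frequency aim contradicts section 8 directly. Objective 2(ii) cannot be met as worded, because enrolment is limited to LRR patients and no comparator is described. There are no recurrence-free patients, so no risk, odds or hazard ratio for developing LRR can be estimated. A statistical analysis plan cannot repair this without outside data that the protocol does not mention.

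The relative risks above show non-identifiability. They are not estimates, and they depend on the assumed source shares. The 15% to 30% capture assumes that the protocol's 33 eligible patients per unit applies to the participating units.

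The size is moderate: it changes what the study may claim, not its main analysis. The DFS comparison, the 330-patient requirement and the prognostic analyses do not depend on it. The era of original treatment is a presentational matter for the guideline comparison, not an established error.

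**What to change.** 1. Delete frequency from the overview and section 2.2, or define it as the number of LRR cases screened at participating units.
2. Reword objective 2(ii), and the matching statements in the overview and section 1.1, to: describe the prevalence of known LRR risk factors, and the original treatment received, among patients with LRR.
3. Add a sentence that no association with, or cause of, LRR development will be inferred from this cohort, including from the guideline comparison in sections 1.2.4 and 4.3.
4. As a secondary suggestion, present the comparison with reference 35 by era of original surgery, using the date already collected as item 2.1. Do not restrict it to recently treated patients: with 24 months of recruitment from November 2021, limiting it to surgery from 2018 onward would keep only intervals below about six years and so select early recurrences.

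The cost is a protocol wording change and, for item 4, a simple grouping by surgery date. No new patients, data items or follow-up are needed. The study gives up a claim that it could not have supported.

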2.4 Study endpoints

2.4.1 Primary endpoint:

DFS following LRR resection in patients who present without distant metastasis, stratified according to the type of surgery performed for the primary breast cancer (BCS and radiotherapy vs. mastectomy).

2.4.2 Secondary endpoint:

-PFS in patients who present with LRR with distant metastasis.

-OS in patients with LRR +/- DM at presentation.

3. Definitions

For the purpose of this study, LRR is defined as diagnosis of invasive breast cancer or ductal carcinoma in situ in the ipsilateral breast (if applicable)/skin/chest wall/regional nodes (axilla/internal mammary/supraclavicular/infraclavicular) following previous breast cancer treatment with curative intent.

4. Methods

This is a prospective observational multicentre longitudinal cohort study. This will be a national research study in collaboration with the Association of Breast Surgery (ABS) Academic and Research committee, the Mammary Fold Academic and Research Collaborative (MFAC) committee, and the UK Breast Cancer Trainees Research Collaborative Group (BCTRCG).

The study will have 3 main phases;

- 1. National practice questionnaire on current management of patients diagnosed with LRR by breast MDTs across UK.
- Development of a national prospective cohort of patients newly diagnosed with LRR
 +/- DM in order to document management details for each patient with respect to their original and recurrent cancer.
- 3. Evaluating oncological outcomes of the study cohort at 3 and 5 years by collation and analysis of the data submitted from the participating centres.

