Descriptive summary statistics will be calculated for each outcome and regression analysis used to control for predictive variables. Data will be tested for distribution and differences between groups using unpaired t-tests, Mann-Whitney U tests and Chi squared tests as appropriate. Based on the NCRAS report described in section 1, approximately 250 patients were diagnosed with LRR with or without distant metastasis across 15 UK breast units over 6 months. This data suggests that around 33 patients will be eligible for recruitment over 12 months in each breast unit. This potential sample size has been corroborated from data at Leeds Teaching Hospitals NHS trust (LTHT) where 28 patients met the eligibility criteria (January 2019 to December 2019). This was based on information from the LTHT cancer information team. There are 144 breast units in the UK and at least 50 units so far have agreed to participate in the study. Given the variable number of cancer patients treated per year in these participating units, we would anticipate each unit to recruit 5 to 10 patients over 12 months. Therefore, we would aim to recruit at least 500 patients diagnosed with LRR +/distant metastasis over 24 months. There are no statistical criteria for stopping the study early as the study is observational in nature examining current UK practice and therefore low risk.

One of the key aim of the study is to determine whether patient prognosis after their LRR diagnosis (without distant metastasis) differs according to the type of breast cancer surgery (mastectomy versus BCS and radiotherapy) for the initial cancer. Based on published studies[36, 37, 39], the distribution of patients presenting with LRR is almost even between mastectomy and BCS for the initial cancer (40% mastectomy and 60% BCS). From these published studies, the 5 year DFS after treatment for LRR has been reported to be approximately 70%[67, 68]. A single centre retrospective study by Shenouda *et al*[39] identified that patients initially treated with BCS and radiotherapy had improved DFS by

approximately 20% as compared to patients initially treated with mastectomy and no radiotherapy (5 year DFS of 80% vs. 60%).

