Power calculation was performed to determine sample size in each group (patients treated with mastectomy versus BCS and radiotherapy for the initial cancer), using logistic regression analysis to adjust for other covariates stated in the background section (tumour and nodal staging, molecular receptor profile, and tumour grade). This calculation has determined that the estimated sample size for each group would be 165 patients. Therefore, a subset of 330 patients diagnosed with LRR without distant metastasis will require recruiting to the study to determine whether patient prognosis differs according to the type of breast cancer surgery performed for the initial cancer. This falls well within the minimum patient recruitment target of 500 patients who are diagnosed with LRR +/- distant metastasis.

Kaplan Meier survival analysis will be performed at the two study time points (3 and 5 years after diagnosis of LRR). We will determine DFS/PFS/OS for the study participants. DFS will be determined for patients diagnosed with LRR without associated distant metastasis at presentation who then subsequently undergo LRR resection. PFS will be determined for patients diagnosed with LRR with associated distant metastasis at presentation. OS will be determined for the whole study cohort (i.e. patients diagnosed with LRR with or without associated distant metastasis at presentation). We will perform Cox proportional hazards regression for multivariate analysis and log-rank tests for univariate analysis, including potential prognostic factors as variables of interest.

9. Publication and authorship policy

All presentations and publications will be made on behalf of the MARECA study steering group. The steering group will be responsible for drafting manuscripts and preparing them for publication. Three levels of authorship are proposed based on degree of study participation:

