Thank you very much for taking time to complete the survey. We are in the process of setting up a national study of **ma**nagement of breast cancer locoregional **re**currence and oncologi**ca**l outcome (the MARECA study). We welcome participation from all UK breast units. Please email the study team ([contact]) to register your interest. We especially welcome participation from trainees.

MARECA study Gantt chart

021	2022	2023	2024	2025	2026	2027	2028	2029	203
			_				_		
MARECA study national practice questionnaire Opened Feb 2021 with 41/60 study centres already completing the survey. Due to complete data return for all units by Aug 2021.	MARECA study national prospective cohort study 60 UK study centres to recruit patients newly diagnosed with breast cancer locoregional recurrence +/- distant metastasis for 24 months. Target recruitment of 500 patients. 330 patients required to determine the study's primary endpoint.			Determination of oncological outcome for the study cohort Study centres to return oncological outcome data at 3 and 5 year follow up.				222 C	
Study submitted for ethics application via IRAS: LTHT study sponsor.	NIHR portfolio adoption and study set up	Data validation and collation for analysis	Oncological outcome data collation and analysis		to / c	Collation of tissue/slide conse to design translational sub-stu / develop national guidelines with ABS		ub-stud	
Nati	ication 1: onal practice tionnaire results	Publication 2: Study Protocol	Results			l outcome o rt / identific	outcome of the / identification

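### The key aim and the 330-patient target cover all patients without distant metastasis, but the primary endpoint and its analysis cover only those later resected

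*Protocol*

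**What the plan says.** Three statements set no resection condition:

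- Protocol section 2.3, objective 2(iii): outcome at 3 and 5 years is "Disease Free Survival (DFS) for patients diagnosed with LRR without associated distant metastasis at presentation".
- Section 8, key aim: "One of the key aim of the study is to determine whether patient prognosis after their LRR diagnosis (without distant metastasis) differs" by the surgery used for the initial cancer.
- Section 8, target: "a subset of 330 patients diagnosed with LRR without distant metastasis will require recruiting to the study".

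Two statements do:

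- The main outcome (section 2.4.1) is "DFS following LRR resection in patients who present without distant metastasis, stratified according to the type of surgery performed for the primary breast cancer".
- Section 8, analysis: "DFS will be determined for patients diagnosed with LRR without associated distant metastasis at presentation who then subsequently undergo LRR resection".

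The Gantt chart in the Appendix links the two sets, giving "330 patients required to determine" the primary endpoint.

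Section 5 records whether the LRR was operated on (item 3.23), the reason if it was not (item 3.24: among others unresectable disease, unfitness, the patient's choice, or systemic therapy begun first) and the date of LRR surgery (item 3.25). Sections 4.4 and 8 place data collection and the Kaplan-Meier analyses at 3 and 5 years after LRR diagnosis. Section 8 assigns progression-free survival to patients with metastasis at presentation and overall survival (OS) to the whole cohort.

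**The concern.** The statements agree only if every non-metastatic patient is resected, and item 3.24 shows that the protocol does not expect this. Three things follow.

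1. The 330 cannot be both the number recruited without metastasis and the number available for the primary endpoint.
2. Unresected non-metastatic patients enter neither the DFS nor the progression-free survival analysis. They appear only in OS, pooled with metastatic patients. The key aim is prognosis after diagnosis by original surgery, and no comparison is specified in the population it names.
3. Resection happens after diagnosis, and some of the listed reasons against it (unresectable, unfit) plausibly carry a worse prognosis. The analysed group is therefore selected. If its time is counted from diagnosis, nobody in it can have died before surgery.

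**Working it through.** **1. The plan's own figure.** Section 8 gives 165 per group, and 2 × 165 = 330, so nothing was added between the calculated number and the recruitment target. The inputs given are 5-year DFS of 80% (breast conserving surgery, BCS, with radiotherapy) and 60% (mastectomy). Alpha, power and the strength of covariate adjustment are not given. The standard formula for two proportions is

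n per group = [z(α/2)·√(2p̄q̄) + z(β)·√(p₁q₁ + p₂q₂)]² / (p₁ − p₂)²

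With p̄ = 0.70, two-sided 0.05 and 80% power (both assumed): (1.960 × 0.648 + 0.842 × 0.632)² / 0.04 = 82 after rounding up. Power of 90% gives 109 and 95% gives 134. A covariate adjustment that divides n by (1 − R²) would reach 165 with R² = 1 − 82/165 = 0.50 at 80% power, or 1 − 109/165 = 0.34 at 90%. So 165 can be neither reproduced nor refuted, and it is taken as given below.

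**2. Number entering the primary analysis.** Let r be the proportion of non-metastatic patients who are resected. The documents give no value, so r is an assumption. The number analysed is 330·r, and the number of non-metastatic recruits needed to have 330 resected is 330/r. Power = Φ{[|p₁ − p₂|·√n − 1.960·√(2p̄q̄)] / √(p₁q₁ + p₂q₂)} with n = 330r/2 per group, unadjusted, equal groups, two-sided 0.05. For example, at r = 0.80, n = 132: (0.20 × 11.49 − 1.270)/0.632 = 1.62, which is 94.8%.

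| r | Analysed from 330 | Recruits needed for 330 resected | Power, 80% vs 60% |
|---|---|---|---|
| 1.00 | 330 | 330 | 98.0% |
| 0.95 | 314 | 348 | 97.5% |
| 0.90 | 297 | 367 | 96.8% |
| 0.80 | 264 | 413 | 94.8% |
| 0.70 | 231 | 472 | 91.8% |

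For a smaller difference, 75% vs 60%, the same formula gives about 83% at r = 1, 79% at 0.90, 74% at 0.80 and 68% at 0.70.

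**3. Effect of selection on the comparison.** For each original-surgery group, the all-patient 5-year rate is r·p + (1 − r)·u, where p is the rate in resected patients and u the rate in unresected patients (assumed 20 to 40%). Take p = 80% after BCS and 60% after mastectomy, a gap of 20 points among resected patients.

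- Resection 95% after BCS and 75% after mastectomy, u = 20%: 0.77 − 0.50 = 27 points.
- Resection 95% and 85%, u = 40%: 0.78 − 0.57 = 21 points.
- Resection 90% in both, u = 20%: 0.74 − 0.56 = 18 points.

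In the first two cases the resected-only comparison understates the all-patient gap. In the third it overstates it. Holding BCS at 95%, the break-even mastectomy share m solves 0.57 − 0.4m = 0.20 (u = 20%) or 0.38 − 0.2m = 0.20 (u = 40%), so m = 92.5% or 90%. The direction turns on resection rates that the protocol does not give.

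**4. Time origin.** The endpoint wording points to resection. The 3- and 5-year analysis points run from diagnosis. If the clock starts at diagnosis, each resected patient contributes an interval before surgery in which death could not have occurred, and that interval is longest when systemic therapy comes first.

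**The case against.** The endpoint itself is clear: sections 2.4.1 and 8 agree on DFS after resection. DFS conventionally starts when a patient is free of disease, and the planning rate in section 8 is DFS after treatment of the LRR, so a resected population is defensible. Objective 2(iii) can be read as the broad statement that the endpoint makes specific. Unresected patients are not lost, since OS covers everyone, Cox models of prognostic factors are planned, and the data are collected. Starting systemic therapy first need not mean never being resected, because item 3.22 foresees neoadjuvant treatment to enable surgery.

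Much of this stands. It supports keeping the resected population, but it does not reconcile the 330 or the key aim with that population.

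Three stronger readings are tempting and are not supported:

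- A reader might infer that selection biases the comparison towards no difference because post-mastectomy recurrence is less often resectable. Section 1.3 describes chest-wall nodules with dermal lymphatic involvement as possibly having a worse prognosis, but says nothing about resectability. Item 3.26 lists excision of skin-flap or chest-wall recurrence, and scenario 4 of the questionnaire describes one. The 21 to 27 point gaps come from assuming lower resection after mastectomy.
- A reader might infer that the primary comparison is underpowered. For the stated 20-point difference, the unadjusted figures do not show this.
- A reader might infer that 165 per group is wrong. Without alpha, power and R² it cannot be judged.

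**Conclusion.** The mismatch is explicit and should be corrected. Two populations serve one question, and the 330 overstates the number that can enter the primary analysis: 264 to 314 if 80 to 95% are resected, which is an assumption. The loss of power for 80% vs 60% is small (98.0% to 94.8% at 80% resected, unadjusted, two-sided 0.05 assumed). The margin is thinner for a smaller difference, or if the 165 already includes covariate adjustment. The main harm is to what the result means: the key aim has no specified analysis in its own population, and the resected comparison may over- or understate the all-patient difference. The unsettled time origin adds guaranteed event-free time if the clock starts at diagnosis.

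**What to change.** - Restate the 330 as resected non-metastatic patients, or keep 330 recruits and state the smaller number expected in the primary analysis. The first option means about 348 to 413 non-metastatic recruits at 95 to 80% resected.
- Reword objective 2(iii) to match section 2.4.1 and the DFS analysis in section 8.
- Start DFS at the date of LRR surgery (item 3.25) and censor at last follow-up. Data collection is fixed at 3 and 5 years after diagnosis, so slightly less than five years from surgery will be observed, and the text should say so.
- Answer the key aim with OS from LRR diagnosis, compared by original surgery, in all non-metastatic patients.
- Report the proportion resected by original surgery, so that readers can judge the selection. This needs only items 2.4, 2.23, 3.19 and 3.23.

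The cost is protocol wording, a slightly less favourable stated number, and one more analysis on data already collected.
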